### Partial Dates for Subsequent Therapy

Incomplete subsequent therapy dates will be imputed. Imputed dates will be used to determine Study Day.

Partial start dates will be imputed as follows:

1. Only the year is reported, with month and day missing: If the subject's last study treatment and subsequent therapy are in the same year, then the date of the last dose of study treatment will be used to impute the start date of the subsequent therapy.
2. The month and year are reported, with day missing: The first day of the month will be used to impute the start of the subsequent therapy.

Partial end dates will be imputed for non-ongoing therapies as follows:

1. Only the year is reported, with month and day missing: the earlier of December 31 or analysis cut-off date will be used to impute the end of the therapy.
2. The month and year are reported, with day missing: The last day of the month will be used to impute the end of the therapy.

End dates for ongoing therapies will be imputed to analysis cut-off date.

If an imputation results in an imputed start date after the stop date, set the date with more imputation to the one with less imputation.

Subsequent anti-cancer therapies will be summarized by part, treatment and will be presented in a listing.

- Any subsequent anti-cancer therapy
- Type of therapy
- Subsequent systemic therapy regimen/agents
- Best response
- Reason for discontinuation

Subsequent procedures and surgeries will be presented in a separate listing.

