^e Patients should have all AEs reported for at least 30 days following the last dose of the G100 study agent. This includes those who withdraw early before completion of the study.

^f Thyroid function tests (including TSH) should be performed at screening in those patients being evaluated to participate and be randomized in Part 2 G100 vs. G100 plus pembrolizumab.

^g Patients will receive telephone follow-up or clinic visit every 8 to 12 weeks after disease progression until 1 year after first study injection. Follow-up will include vital status (survival), cancer status (e.g., lymphoma transformation), and post-treatment anti-cancer therapy including time to next treatment, treatment details, and clinical response. If the patient agrees, the site may periodically (e.g. every 2 to 4 months) contact the patient beyond 1 year to check on vital and cancer status.

^h Imaging studies during Follow-up will occur on Day 112, every 8 weeks thereafter for the first year, every 3 to 4 months for the second year, and then at least every 6 months for the third and subsequent years.

Immune Design

G100 (GLA-SE) and Pembrolizumab or Rituximab

Protocol IMDZ-G142; Version 04B; November 15, 2018

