### 5.6.5 Overall Survival (OS)

Overall Survival (OS) is defined as the time from date of first study treatment to death due to any cause. Overall survival in months is calculated as:  $(\text{date of death} - \text{date of first dose}) + 1) / 30.4375$ . Patients who are alive at the end of study will be censored at the last date the patient is known to be alive or data analysis cutoff date, whichever is earlier.

Summary of OS including median, 95% CI, 25th and 75th percentiles, and range will be estimated using the Kaplan-Meier method. The corresponding 95% CI for median will be calculated using the Brookmeyer and Crowley method. The Kaplan-Meier survival curve will be displayed.

OS data will be presented in a data listing.

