## **5.6.7 Time to Next Treatment and Duration of All Subsequent Therapies**

Time to next treatment is defined as the time from the date of first study treatment to the start date of subsequent therapy after PD. Patients who did not receive subsequent therapy after PD are censored at the date of last contact or death.

Duration of all subsequent therapies after PD in week is calculated as (date of subsequent therapies last administered – date of subsequent therapies first administered + 1)/7. If one patient has multiple consecutive systemic therapies, the duration will be summarized per patient. If the start and end dates of multiple systemic therapies overlap, then duration = (date of last systemic therapy last administered – date of first systemic therapy first administered + 1)/7.

Summary of time to next treatment including median, 95% CI, 25th and 75th percentiles, and range will be estimated using the Kaplan-Meier method. The corresponding 95% CI for median will be calculated using the Brookmeyer and Crowley method. Descriptive statistics using PROC UNIVARIATE of time to next treatment and duration of all subsequent therapies including only patients with subsequent anti-cancer therapies will also be reported.

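### SAP 5.6.7 sets the end of an ongoing subsequent therapy to the analysis cut-off and summarises the duration as complete, which can overstate or understate it depending on when contact ended

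*SAP*

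**What the plan says.** SAP 5.6.7 defines the duration in weeks. The formula begins "Duration of all subsequent therapies after PD in week is calculated as (date of subsequent therapies last administered", subtracts the date first administered, adds one day and divides by 7. Consecutive therapies are combined per patient. The summary is "Descriptive statistics using PROC UNIVARIATE of time to next treatment and duration of all subsequent therapies including only patients with subsequent anti-cancer therapies". Kaplan-Meier is specified in that section only for time to next treatment.

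Under Partial Dates for Subsequent Therapy, the rule for a therapy still running is "End dates for ongoing therapies will be imputed to analysis cut-off date". For a finished therapy with only the year known, "the earlier of December 31 or analysis cut-off date will be used to impute the end of the therapy"; with month and year known, the last day of the month is used. None of these is limited by last contact or death. The use stated for imputed dates is "Imputed dates will be used to determine Study Day".

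Neighbouring rules do have such a limit. For time to next treatment, "Patients who did not receive subsequent therapy after PD are censored at the date of last contact or death". For overall survival (SAP 5.6.5), living patients are "censored at the last date the patient is known to be alive or data analysis cutoff date, whichever is earlier".

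On follow-up, the schedule footnotes in the protocol (for example 3.2, footnote g) say "Patients will receive telephone follow-up or clinic visit every 8 to 12 weeks after disease progression until 1 year after first study injection", with optional later contact about vital and cancer status. The Safety Monitoring text (protocol synopsis and 4.7) allows more than a year if the patient agrees, and includes later anti-cancer therapy and its details in what is ascertained. For Parts 4 and 5, protocol 10.3.22.2 and 10.3.29.2 describe one year as a minimum.

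**The concern.** For a patient whose last contact came before the cut-off, a therapy marked as ongoing is known to have continued only to that contact. Carrying it to the cut-off turns elapsed calendar time into treatment time. PROC UNIVARIATE then treats the result as an observed end.

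The added time depends on when contact ended relative to the cut-off, not on the therapy. SAP 5.6 calls for results by part, and the parts opened in sequence, so differences in this summary between parts could reflect enrolment date. Protocol version 01 is dated 12 March 2015 and version 04B 15 November 2018, about 44 months apart (3 years 8 months). A long gap for the earliest patients is therefore possible, although the documents give no enrolment dates.

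At stake is whether one descriptive summary can be read as it is labelled.

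**Working it through.** The plan states no figure for this duration, so there is none to reproduce. The steps below apply its rule.

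**1. One patient.** Inputs from the SAP: duration = (end − start + 1)/7, with end = cut-off if ongoing. Assumed: therapy starts on Day 200 and is ongoing at last contact on Day 365. Observed: (365 − 200 + 1)/7 = 23.7 weeks.

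| Cut-off | Duration under the rule (weeks) | Excess (weeks) |
|---|---|---|
| Day 365 | 23.7 | 0 |
| Day 730 | 75.9 | 52.1 |
| Day 1095 | 128.0 | 104.3 |
| Day 1460 | 180.1 | 156.4 |

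The excess over the observed time is (cut-off − last contact)/7, whatever the start date. It is zero when contact reaches the cut-off. The value is then an incomplete duration counted as complete.

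**2. A group.** Assumed, with no source in the documents: starts uniform over months 4–12, exponential therapy length with mean m months, therapy status known only to month 12, cut-off at month c.

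- Share ongoing at month 12: p = (m/8)(1 − e^(−8/m)), which is 0.43, 0.55 and 0.66 for m = 4, 6 and 9.
- Mean time on therapy observed by month 12: m(1 − p).
- Mean reported under the rule: m(1 − p) + p(c − 12) months, multiplied by 30.4375/7 for weeks.
- Error in the reported mean: p(c − 12 − m) months.

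For m = 6 and c = 36: 6 × 0.448 + 0.552 × 24 = 15.94 months, or 69.3 weeks.

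| Mean length (true mean, weeks) | c = 18 | c = 24 | c = 36 | c = 42 |
|---|---|---|---|---|
| 4 months (17.4) | 21 | 32 | 55 | 66 |
| 6 months (26.1) | 26 | 40 | 69 | 84 |
| 9 months (39.1) | 30 | 48 | 82 | 100 |

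The last formula explains the pattern. The mean is overstated when the gap from last contact to cut-off exceeds the mean remaining therapy time, is right by coincidence when they are equal (6 months, cut-off 18), and is understated when the gap is shorter (9 months, cut-off 18).

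**3. Medians.** Simulating the same model, the 6-month case gives reported medians of 28, 54, 106 and 132 weeks for the four cut-offs, against a true 18. The 4-month case gives 17.5 weeks at every cut-off, against a true 12. The median becomes very large only when more than half of the patients are marked ongoing.

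**4. Moving the end date is not enough.** Stopping the clock at month 12 and still treating the result as complete gives means of m(1 − p): 9.9, 11.7 and 13.2 weeks against 17.4, 26.1 and 39.1. Censoring is needed as well.

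**The case against.** Several stronger readings are tempting and are not supported.

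- **That therapy status is never known after one year.** The schedule footnotes alone suggest this. The Safety Monitoring text allows longer follow-up that covers therapy details if the patient agrees, and the Part 4 and 5 procedures set one year as a minimum. For patients followed longer the gap shrinks or disappears. The month-12 stop used above is an assumption.
- **That every ongoing therapy is overstated.** Overrun needs last contact or death before the cut-off. Otherwise the error is an understatement.
- **That the SAP says the imputed end dates feed the duration.** It names only Study Day. The inference is reasonable: the rule sits in 5.6.7, whose duration formula needs an end date, and SAP 5.2 refers to the subsequent-therapy section for these dates. It is still an inference.
- **That patients will be credited with therapy after death.** This requires a deceased patient's record to remain marked ongoing. The rule does not prevent it, but nothing shows that it would survive data cleaning.

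It is also fair to say that duration of subsequent therapies is not a protocol objective or endpoint, that subsequent therapies are listed as well as summarised, and that a missing day of the month can add only about 30 days.

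What stands is that the rule as written has no bound and no censoring, while the rules for overall survival and time to next treatment in the same SAP stop at what was observed.

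**Conclusion.** The point holds as a minor defect in a descriptive output. Followed as written, and assuming that imputed end dates enter the duration, the rule misstates it in either direction. It adds (cut-off − last contact or death)/7 weeks when contact or life ended before the cut-off, and understates when the patient was still in contact and on therapy at the cut-off.

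The size cannot be fixed from the documents. Under the stated model the reported mean runs from below the truth (30 against 39 weeks) to several times it (66 against 17), depending on therapy length and cut-off. A reader should not take the large figures alone as the expected error.

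The end-date rule does not affect time to next treatment, response results, sample size or any decision rule.

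**What to change.** Replace the ongoing-therapy sentence in SAP 5.6.7 with wording to this effect:

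- If the patient died while on a therapy recorded as ongoing, the duration ends at the date of death and counts as complete, because death ends therapy.
- Otherwise the duration is censored at the earlier of the analysis cut-off and the last contact at which the patient was recorded as on therapy (or the last contact date, if that is not captured).
- Imputed partial end dates are capped at the earliest of death, last contact and cut-off.
- Imputed end dates are used in the duration as well as for Study Day.

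Summarise one duration per patient, from the first start to the end of the last therapy, by Kaplan-Meier. Alternatively, give descriptive statistics for completed durations and report the number ongoing separately.

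The cost is SAP wording and minor programming. No passage specifies a dated therapy-status field, hence the fallback to last contact. The downside is that some medians may not be estimable. In a simulation of 20 patients (starts on Days 100–330, contact ending on Day 365, exponential durations), the Kaplan-Meier median was not reached in 1%, 31% and 77% of runs for true medians of 13, 26 and 52 weeks. If that is likely, the separate report of completed and ongoing therapies is the more useful display.

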### **5.6.8 Immune Response and Biomarker Analyses**

All patients who have received at least one injection of G100 and have available immunohistochemistry (IHC), nanostring, or T cell receptor (TCR) data will be included in the biomarker analysis.

Anti-tumor cellular immunity (CD4, CD8 T cell, CD20, CD68, NKp46, FoxP3, CD8/CD4 ratio, CD8/FoxP3 ratio) by immunohistochemistry (IHC) will be explored. Post/pre treatment ratio will be summarized by treatment, and by subgroups of interest (irPR vs non-responder, pre-TLR4 $\geq$ 50% vs <50%, treatment naïve, relapsed/refractory patients, prior line of therapy 0-2 vs  $\geq$ 3). Post and pre treatment values will be compared using signed-rank test to identify significant changes post treatment. Association between clinical endpoints (irPR, irPR+MR, irPR+MR+SD, abscopal best % change better than -25%) and cellular immunity by immunohistochemistry will be explored using a logistic regression model for all dosed patients, and by treatment. Association between response (irPR) and pre-treatment TLR4 using different cutoffs will be presented in 2x2 tables and the proportion of response will be compared between TLR4 high and TLR4 low patients using Barnard's unconditional exact test. Comparison of post treatment change in immunohistochemistry will be explored between G100 monotherapy 10  $\mu$ g and G100 monotherapy 20  $\mu$ g patients.

Association between clinical response and nanostring genes (NK, M1 Markers, M2 Markers, and other genes of interest) using PBMC and tumor samples will be explored using a logistic regression model that includes  $\log_2$  transformed nanostring data. Post/pre mean expression ratio (as antilogarithm of the means of ( $\log_2$  post –  $\log_2$  pre)) for responder and non-responder, odds ratio, and nominal and adjusted p-values will be presented. Adjusted p-value is adjusted using False Discovery Rate (FDR) method. Ten most upregulated and ten most downregulated immune-related genes will be presented, with post/pre mean expression ratio and p-value from signed-rank test. Further, ten most highly differentially induced immune-related genes in clinical responders versus non-responders will be explored.

T cell receptor (TCR) clones not detectable at baseline in tumor/PBMC but become detectable or increased post-treatment in tumor/PBMC will be explored.

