^c Pregnancy test should only be performed on FCBP. Urine pregnancy test is recommended and must be performed (and negative) within 7 days prior to starting study treatment, Day 14 prior to the first dose of pembrolizumab, and day 77. Site may use serum pregnancy test if part of their procedures. For patients in the UK and France, urine pregnancy tests must also be performed every month or sooner while the patient is receiving G100.

^d For the pre-treatment tumor biopsy, baseline excisional or core biopsy should be obtained from the treatment target lesion or non-target lesion (preferably near the target lesion). Post-treatment tumor biopsy should be performed on Day 56 +/- 7 days for patients not receiving optional treatment #9. If a 9th dose is given, then biopsy should be delayed to Day 63 to 77. The biopsies should be performed on the treated tumor if feasible. If the primary treated site is not available, a different site should be chosen. **The biopsy site location and whether or not it was treated with G100, radiation, or was an abscopal site must be recorded/documented.**

^e For patients enrolled on the pembrolizumab arm, all adverse events experienced from the time of enrollment through 30 days following cessation of treatment will be reported by the investigator. Any event of clinical interest (ECI) experienced through 30 days following cessation of treatment should be reported within 24 hours to the Sponsor. Any SAE due to any cause other than progression of the cancer under study that occurs through 90 days following cessation of pembrolizumab treatment, or 30 days following cessation of treatment if the subject initiates new anticancer therapy, whichever is earlier, must be reported within 24 hours to the Sponsor. After the 90-day reporting period, any SAE that comes to the attention of the site staff that may be causally related to study drug (i.e., the event is considered possibly, probably or definitely caused by the drug) must be reported to Sponsor regardless of time elapsed.

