Urinalysis		X												
Pregnancy test ^c		X			X							X	X ^e	
G100 dosing			X	X	X	X	X	X	X	X	X			
Pembrolizumab dosing					X			X			X	X	X	
Tumor biopsy	X ^d										X ^d	X ^d		
Clinical Status														X ^g
Blood volume per visit (mL)		25	30	10	30	10	10	10	10	10	15	10		
Total blood volume ^j		25	55	65	95	105	115	125	135	145	160	170		

Immune Design

G100 (GLA-SE) and Pembrolizumab or Rituximab

Protocol IMDZ-G142; Version 04B; November 15, 2018

- ^a Physical exam also includes tumor measurements of treated and any untreated lesions measurable by exam. If appropriate, photographs should be taken to document lesions.
- ^b Thyroid function tests (including TSH) should be performed at screening and then every 6 weeks (following initiation of pembrolizumab) or as indicated by patient symptoms during pembrolizumab therapy to screen for immune mediated thyroid changes.
- ^c Pregnancy test should only be performed on FCBP. Urine pregnancy test is recommended and must be performed (and negative) within 72 hours (3 days) prior to starting G100 and then before pembrolizumab on Day 14, and on day 77. Site may use serum pregnancy test if part of their procedures. In UK and France, urine pregnancy tests must also be performed every month or sooner while receiving G100 and/or pembrolizumab.
- ^d For the pre-treatment tumor biopsy, baseline excisional or core biopsy should be obtained from the treatment target lesion or non-target lesion (preferably near the target lesion). Post-treatment tumor biopsy should be performed as close to 2 weeks following the last dose of G100 as possible: on Day 42 to 56 for patients receiving 6 doses if G100 or, if a 9th dose is given, then biopsy should be delayed to Day 63 to 77. The biopsies should be performed on the treated tumor if feasible. If the primary treated site is not available, a different site should be chosen. **The location of the biopsy site and whether or not it was treated with G100 or was an abscopal site must be recorded/documentated. If the patient has both treated and untreated tumor sites amenable to biopsy, separate biopsies of each site should be performed.**

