10.3.8 Visit 11: Clinical Assessment and Optional G100 Dose # 9 (Day 56)

This is a mandatory Clinical Assessment visit. For patients whose treated tumor has not regressed completely, 3 optional treatments may continue and the final dose #9 may be given on this visit. Note that on each immunization day, all procedures and blood draws must be done before dosing. The following will be completed:

- 1) Review of AEs and SAEs
- 2) Recording of any previous / concomitant medications
- 3) Vital signs
- 4) Symptom-directed physical exam
- 5) Assessment and measurements of tumor treated with G100 and measureable untreated distal tumor lesions by exam
- 6) ECOG status
- 7) Safety labs as in [Section 10.3.2 – Hematology, Clinical chemistry](#)
- 8) For patients in Part 1 and Part 2, blood for cell phenotyping / profiling (not collected in Part 3)
- 9) Blood for T cell gene profiling
- 10) For patients in the UK, urine pregnancy test
- 11) Assessment of disease including CT or MRI of chest, abdomen, pelvis. Other assessments such as CT of the head, body PET CT, or bone marrow biopsy should be performed if indicated. Day 56 (+/- 7 days) restaging CT or MRI scans should be performed if the optional treatment #9 is not given. If the 9th dose is given, then imaging studies should be delayed to Day 63 to 77. If a PET CT is used, a standard high resolution CT series should be obtained rather than low resolution scans for tumor measurements. However, PET scans should not be used to determine disease progression since it is expected that PET avidity will increase with the type of inflammation induced by this treatment and may lead to false positive results.

- 12) Photographs: if the tumor can be measured and assessed visually, photographic documentation with measurements should be considered in order to keep a record and help assess any response to treatment (may be performed at any time during study)
- 13) Post Treatment tumor biopsy. Post-treatment tumor biopsy of available tumor (treated or untreated tumor to investigate systemic response) should be performed on Day 56 +/- 1 week for patients not receiving optional treatment #9. If the 9th dose is given, then the biopsy should be delayed to Day 63 to 77. The biopsies should be performed on the treated tumor if feasible; if not available, a different site should be chosen. The location from where the sample was obtained (treated, non-treated, irradiated or non-irradiated, untreated distal site) must be recorded.

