## **7 Adjustment for Covariates**

In exploratory analyses comparing post treatment change in immunohistochemistry immune infiltrate between G100 monotherapy 10 µg and G100 monotherapy 20 µg patients, pre-treatment TLR4 and pre-treatment CD8/CD4 ratio are included as covariates in the analysis of variance model.

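### SAP 5.6.8 pools paired tumor biomarker samples without using biopsy site, so post/pre changes mix local and abscopal effects and comparisons with response can be confounded

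*SAP*

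**What the plan says.** **Analysis.** The biomarker set in SAP 5.6.8 is "All patients who have received at least one injection of G100 and have available immunohistochemistry (IHC), nanostring, or T cell receptor (TCR) data", with no condition on where the biopsy was taken. "Post/pre treatment ratio will be summarized by treatment, and by subgroups of interest"; the subgroups listed are response, baseline TLR4, treatment-naive or relapsed/refractory status, and prior lines. "Post and pre treatment values will be compared using signed-rank test to identify significant changes post treatment". Associations of the immunohistochemistry (IHC) markers with four clinical endpoints "will be explored using a logistic regression model for all dosed patients, and by treatment". The tumor nanostring models have no site term either. For the 10 versus 20 µg comparison, SAP 7 says only that "pre-treatment TLR4 and pre-treatment CD8/CD4 ratio are included as covariates in the analysis of variance model".

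**Sampling.** Under Protocol 3.3 footnote d, the baseline biopsy comes from the target lesion or from a non-target lesion, preferably nearby. The post-treatment biopsy comes from the treated tumor if feasible, but: "If the primary treated site is not available, a different site should be chosen". Protocol 10.3.8 item 13 admits treated or untreated tumor and adds: "The location from where the sample was obtained (treated, non-treated, irradiated or non-irradiated, untreated distal site) must be recorded". For Part 4 (Protocol 3.5 footnote d): "If the patient has both treated and untreated tumor sites amenable to biopsy, separate biopsies of each site should be performed". Protocol 3.6 footnote d has the same rule for Part 5. The SAP's own schedule tables repeat the recording requirement.

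**Contrast within the SAP.** SAP 5.6.2 reports tumor response separately for irradiated, non-irradiated and abscopal sites, and SAP 5.6.1 plots abscopal lesions separately. SAP 5.6.8 makes no such split.

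**The concern.** G100 is injected into a lesion and, in Parts 1 to 3, that lesion is irradiated as well. A change measured there and a change measured in a distant untreated lesion answer different questions: local effect and systemic effect. A single post/pre ratio over both has no clear meaning unless the mix of sites is known.

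The comparison with response raises a second issue. Protocol 8.1.4 expects the injected mass to regress and allows G100 to stop once the lesion is too small or inaccessible. A shrunken lesion is also a plausible reason for biopsying elsewhere, and shrinkage defines response. Site and response could therefore be linked without any biological link between marker and response.

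These results carry some weight. Protocol 6.1 cites CD8 infiltrates and their association with response in support of Part 4, and lists biomarker data among the inputs to the Part 5 dose choice. There is also a plain specification gap: with two post-treatment samples from one patient, two programmers could follow the SAP and obtain different paired results.

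The point covers tumor IHC, tumor nanostring and tumor T cell receptor data. It does not cover blood samples, or baseline TLR4 as a predictor.

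**Working it through.** The documents give no sample size, error rate or site mix for these analyses, so there is no plan figure to reproduce. Every number below is an assumption or follows from one.

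**1. Pooled ratio.** Let L be the post/pre ratio in injected lesions, A the ratio elsewhere, and s the share of post-treatment samples from injected lesions. On the log scale the pooled (geometric mean) ratio is L^s × A^(1−s).

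- L = 2, A = 1, s = 0.6: 2^0.6 = 1.52.
- L = 2, A = 1, s = 0.8: 2^0.8 = 1.74.
- L = 2, A = 1.5, s = 0.6: 1.516 × 1.5^0.4 = 1.78.
- L = 2, A = 1.5, s = 0.8: 1.741 × 1.5^0.2 = 1.89.

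The pooled ratio is a mixture even if the site mix is identical in responders and non-responders.

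**2. Responders versus non-responders, no true link.** With injected-site shares sR and sN, the apparent responder/non-responder ratio is (L/A)^(sR − sN). For L = 2, A = 1, sR = 0.4, sN = 0.8, the group ratios are 2^0.4 = 1.32 and 2^0.8 = 1.74. Their quotient is 2^(−0.4) = 0.76.

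Rejection rates were simulated for 9 responders and 21 non-responders, natural-log SD 0.6, and a two-sided 5% Wilcoxon rank-sum test. That test stands in for the planned logistic regression.

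| sR / sN | L | A | Apparent ratio | Rejects |
|---|---|---|---|---|
| 0.4 / 0.8 | 2 | 1 | 0.76 | about 16% |
| 0.8 / 0.4 | 2 | 1 | 1.32 | about 14% |
| 0.6 / 0.8 | 2 | 1 | 0.87 | about 7% |
| 0.4 / 0.8 | 2 | 1.5 | 0.89 | about 7% |
| 0.6 / 0.8 | 2 | 1.5 | 0.94 | about 5% |
| equal | 2 | 1 | 1.00 | about 4% |

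**3. Effect of a site term.** A separate simulation used a linear contrast, 25 or 40 pairs, 40% responders, SD 1 on the log2 scale and A = 1. With untreated-site shares of 60% in one response group and 20% in the other, the unadjusted test rejected in 13 to 20% of runs for L = 2 and 29 to 44% for L = 4. With a 40%/20% split it rejected in 7.5 to 15% over both values of L. Adding a site term brought every setting back to about 5% and the apparent ratio to about 1.0.

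**The case against.** Much of the case against a stronger claim stands.

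- **Site mix and direction.** A reader might infer that responders are more often sampled at untreated sites, so that the response comparison is in fact confounded. No section says so. Protocol 8.1.4 expects regression from radiation in Parts 1 to 3 generally, and untreated lesions may also shrink in responders. A different site need not be untreated, because several masses may be irradiated and injections may be moved within the field. The rule preferring the treated tumor also limits the mixing.
- **No effect elsewhere.** A = 1 runs against the trial's premise: Protocol 4.4 expects systemic immunity and regression of distal lesions. A 1.5-fold abscopal rise takes the 16% down to about 7%.
- **Direction of harm.** If responders were sampled elsewhere more often, their increase would look smaller. That would hide the association the protocol reports, not create it.
- **Dose comparison.** A reader might infer that the 10 versus 20 µg comparison is biased. The site term is missing there too, but nothing suggests that site mix differs by dose.
- **Stronger remedies.** A reader might want the main analysis limited to injected lesions. Under the 40%/80% split that keeps about 4 of 9 responders (0.4 × 9 = 3.6) and 17 of 21 non-responders (0.8 × 21 = 16.8), which is itself selection by response. A site term in the main response model would adjust for something that may result from response, with few events.
- **Stakes.** SAP 8 labels the study exploratory with nominal p-values and false-discovery adjustment for nanostring. SAP 1 defers programming rules to dataset specifications that are not public, so a sample-selection rule may exist there.

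None of this supplies a site stratum or a sample-selection rule in the SAP text. Multiplicity adjustment does not separate a local from an abscopal effect.

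**Conclusion.** The omission is established from the text: SAP 5.6.8 and SAP 7 do not use biopsy site for paired tumor data, although the sampling rules allow mixed sites and the site must be recorded. It follows that the pooled ratio and signed-rank test describe a mixture whenever more than one site type is sampled and the effects differ.

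Confounding of the response comparison is possible, not shown. It needs a site mix that differs by response, which the documents neither give nor exclude, and it could run either way. On a 2-fold local rise with 9 versus 21 patients, the illustration runs from about nominal to 16%. Larger effects or more patients would raise the upper end, and an equal mix removes the bias. Bias in the 10 versus 20 µg comparison is likewise not shown.

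The change is worthwhile but of modest priority, because no primary conclusion rests on these exploratory analyses.

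**What to change.** In SAP 5.6.8, with a cross-reference in SAP 7:

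1. Classify each pre/post pair by site type in exclusive categories: injected; irradiated but not injected; untreated (abscopal). Flag pairs whose baseline sample came from a different lesion.
2. Present post/pre ratios and signed-rank tests separately for injected-lesion pairs and untreated-site pairs, beside the pooled result.
3. Use one sample per patient per site type, and state which sample enters the pooled analysis when two post-treatment biopsies exist.
4. Tabulate the site mix by response group and by dose group, so that readers can judge whether confounding is plausible.
5. Repeat the response and 10 versus 20 µg comparisons within site type, or with a site term, as a sensitivity analysis and not as the required main model.

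The cost is some SAP wording, one variable that is already required, and a few more tables. Each stratum will hold fewer pairs, so its estimates will be less precise.
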